APPENDIX 2 MISSING AND PARTIAL RADIOTHERAPY AND SURGERY DATES IMPUTATION ALGORITHMS

Procedures – Imputation Rules.

If reported procedure start date is a full valid date then set start date equal to the date part of procedure start date.

In case of partial date use imputation rules described below:

- If only day is missing then
 - If month and year of procedure match month and year of first dose date then impute as date of first dose;
 - If month and year of procedure don't match month and year of first dose date then impute as first day of that month and year.
- If both day and month are missing, then impute as maximum between 01JAN of the year and date of the first dose;
- If date is completely missing or invalid then leave missing.

Note: Imputation is not applicable to data where start date is not collected (for example "PRIOR RADIOTHERAPY" CRF). Set start date to missing in this case.

If reported end date is a full valid date then set end date equal to the date part of the reported end date.

In case of partial date use imputation rules described below:

- If reported end date is partial then set end date equal to the last possible reported end date based on the partial entered reported end date.
- If reported end date is missing, continuing, unknown or invalid then set end date equal to the most recent database extraction date.

If end date was imputed then compare end date to the death date or last known alive date if subject is not dead. If posterior then end date should be imputed to death date (or last known alive date if subject not dead).

Note: Imputation of partial dates only applies to data entered on "RADIOTHERAPY" CRF page. For other CRF pages in case of partial dates set end date to missing.

Surgeries – Imputation Rules.

If reported surgery date is a full valid date then set start date equal to the date part of surgery date.

[figure not shown]
In case of partial date, use one of the two imputation rules described below:

[figure not shown]
A. For data collected on "PRIOR SURGERY RELATED TO CANCER" CRF page:

[figure not shown]
- If only day is missing then impute as the first day of the month;
- If both day and month are missing then then impute as 01JAN of the year;
- If date is completely missing or invalid then leave missing.

B. For data collected on other CRF pages (deemed to be on-treatment/subsequent surgeries):

[figure not shown]
- If only day is missing then
 - If month and year of surgery match month and year of first dose date then impute the missing date as the date of first dose;
 - If month and year of surgery don't match month and year of first dose date then impute as first day of that month and year;
- If both day and month are missing then impute as maximum between 01JAN of the year and date of the first dose;
- If date is completely missing or invalid then leave missing.

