4.1.1 Objective Response Rate

Objective Response Rate (ORR) is defined as the number of randomized subjects who achieve a best response of confirmed complete response (CR) or confirmed partial response (PR) based on BICR assessments (using RECIST v1.1 criteria) divided by the number of all randomized subjects. If the objective is for a particular population (LAG3 positive, LAG3 negative), only that population is selected. Best Overall Response (BOR) is defined as the best response, as determined by the BICR, recorded between the date of randomization and the date of objectively documented progression per RECIST v1.1 criteria or the date of subsequent therapy (including tumor-directed radiotherapy and tumor-directed surgery), whichever occurs first. For subjects without documented progression or subsequent therapy, all available response designations will contribute to the BOR determination. Confirmation of response is required at least 4 weeks after the initial response.

When the objective is specific to the investigator assessment, the above definition is altered to exchange BICR for investigator assessment in the derivation of the endpoint.

Time to Response

Time to Response (TTR) is defined as the time from randomization to the date of the first confirmed documented response (CR or PR), as assessed by the BICR. TTR will be evaluated for responders (confirmed CR or PR) only.

When the objective is specific to the investigator assessment, the above definition is altered to exchange BICR for investigator assessment in the derivation of the endpoint.

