4.1.3.1 Primary Definition of Progression-Free Survival (Accounting for Subsequent Therapy)

The primary definition of PFS (PFS truncated at subsequent therapy) is defined as the time between the date of randomization and the date of first documented tumor progression, based on BICR assessments (per RECIST v1.1 criteria), or death due to any cause, whichever occurs first.

Subjects who die without a reported progression will be considered to have progressed on the date of their death. The following censoring rules will be applied for the primary definition of PFS:

- Subjects who did not progress or die will be censored on the date of their last evaluable tumor assessment.
- Subjects who did not have any on study tumor assessments and did not die will be censored on their date of randomization.
- Subjects who receive subsequent anti-cancer therapy prior to documented progression will be censored at the date of the last evaluable tumor assessment conducted on or prior to the date of initiation of the subsequent anti-cancer therapy.

- Subjects who did not have a documented progression and received subsequent anti-cancer therapy will be censored at the date of the last evaluable tumor assessment conducted on or prior to the initiation of the subsequent anti-cancer therapy.

Censoring rules for the primary definition of PFS (PFS truncated at subsequent therapy) are presented as follows and in Table 4.1.3.1-1.

Figure 4.1.3.1-1: PFS Primary Definition

[figure not shown]

Table 4.1.3.1-1: Censoring Scheme used in Primary Definition of PFS

Situation	Date of Progression or Censoring	Outcome
No baseline tumor assessments*	Date of randomization	Censored
No on study tumor assessments and no death*	Date of randomization	Censored
Subsequent anti-cancer therapy started without death or progression per RECIST v1.1 reported prior or on the same day	Date of last evaluable tumor assessment prior to or on the date of initiation of the subsequent anti-cancer therapy	Censored
Documented progression per RECIST v1.1 and no new anti-cancer started before	Date of the first documented progression per RECIST v1.1 (excludes clinical progression)	Progressed

Table 4.1.3.1-1: Censoring Scheme used in Primary Definition of PFS

Situation	Date of Progression or Censoring	Outcome
No progression and no death, and no new anti-cancer therapy started	Date of last evaluable tumor assessment	Censored

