9 CONVENTIONS

The following conventions may be used for imputing partial dates for analyses requiring dates:

- For missing and partial adverse event onset dates, imputation will be performed using the Adverse Event Domain Requirements Specification¹⁶
- For missing and partial adverse event resolution dates, imputation will be performed as follows:
 - If only the day of the month is missing, the last day of the month will be used to replace the missing day. If the imputed date is after the death date or the last known alive date, then the latest known alive date or death date is considered as the resolution date.
 - If the day and month are missing or a date is completely missing, it will be considered as missing.
- Missing and partial non-study medication domain dates will be imputed using the derivation algorithm described in 4.1.3 of BMS Non-Study Medication Domain Requirements Specification¹⁷.
- Missing and partial radiotherapy and surgery dates will be imputed using algorithm described in [APPENDIX 2](#).
- For death dates, the following conventions will be used for imputing partial dates:
 - If only the day of the month is missing, the 1st of the month will be used to replace the missing day. The imputed date will be compared to the last known alive date and the maximum will be considered as the death date.
 - If the month or the year is missing, the death date will be imputed as the last known alive date.
 - If the date is completely missing but the reason for death is present, the death date will be imputed as the last known date alive.
- For date of progression after start of study therapy, the following conventions will be used for imputing partial dates:
 - If only the day of the month is missing, the 1st of the month will be used to replace the missing day. In case of the date of death is present and complete, the imputed progression date will be compared to the date of death. The minimum of the imputed progression date and date of death will be considered as the date of progression.
 - If the day and month are missing or a date is completely missing, it will be considered as missing.

- For date of progression to prior therapies, the following conventions will be used for imputing partial dates:
 - If only the day of the month is missing, the 1st of the month will be used to replace the missing day.
 - If the day and month are missing or a date is completely missing, it will be considered as missing.

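### Partial radiotherapy and surgery start dates are imputed as early as the entry allows, floored only at first dose, so a year-only date can discard a confirmed response and a missing day can turn a PFS event into censoring

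*SAP*

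**What the plan says.** SAP Section 9 makes Appendix 2 the operative rule: "Missing and partial radiotherapy and surgery dates will be imputed using algorithm described in" that appendix. For radiotherapy and other procedures there are three cases:

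- Day missing, month of first dose: "If month and year of procedure match month and year of first dose date then impute as date of first dose".
- Day missing, any other month: "impute as first day of that month and year".
- Day and month missing: "If both day and month are missing, then impute as maximum between 01JAN of the year and date of the first dose".

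Part B of the surgery rules, for surgeries other than prior cancer surgery, repeats the scheme: "If both day and month are missing then impute as maximum between 01JAN of the year and date of the first dose". Completely missing dates stay missing.

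These dates feed two efficacy derivations. SAP 4.1.1 ends the best-response window at progression or "the date of subsequent therapy (including tumor-directed radiotherapy and tumor-directed surgery), whichever occurs first". SAP Table 4.1.3.1-1 censors primary-definition PFS at the last evaluable scan on or before therapy start in this situation: "Subsequent anti-cancer therapy started without death or progression per RECIST v1.1 reported prior or on the same day". The PFS section does not define subsequent anti-cancer therapy. Reading it to include radiotherapy and surgery rests on 4.1.1 and on 7.4.3.2, which lists both among subsequent therapies. SAP 4.1.2 applies similar censoring to duration of response.

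**The concern.** Radiotherapy or surgery given after study treatment is often a reaction to progression. Dating it as early as possible can place it before the progression that led to it, or before the scans that established a response. The plan then treats valid later scans as contaminated by other therapy.

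The SAP does check other imputed dates. Section 9 compares an imputed death date with the last known alive date, and an imputed progression date with death. Appendix 2 compares imputed end dates with death or last known alive. An imputed procedure start is bounded only by first dose, although it is the date that can cancel a response or an event.

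The primary endpoint, BICR ORR in LAG-3 positive participants, is exposed, and so are primary-definition PFS and duration of response. If a procedure truly began on or after first dose, the imputed date cannot be later than the true one. Responses and PFS events can therefore be lost but not gained.

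**Working it through.** The documents state no figure that depends on this rule, so there is none to reproduce. The check applies the rules to dates.

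**One participant (illustrative dates, scans every 6 weeks as in the protocol).** Randomized 04MAR2019; first dose 05MAR2019; PR on 15APR, 27MAY and 08JUL (Weeks 6, 12, 18); PD on 19AUG (Week 24); radiotherapy truly on 26AUG2019. Time = date − randomization + 1.

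| Recorded as | Imputed start | Primary-definition PFS | Best response |
|---|---|---|---|
| 26AUG2019 | 26AUG2019 | Event, day 169 | Confirmed PR |
| AUG2019 | 01AUG2019 | Censored at 08JUL, day 127 | Confirmed PR |
| 2019 | max(01JAN2019, 05MAR2019) = 05MAR2019 | Censored at randomization, day 1 | No on-study scan in window: non-responder |

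In the last row the table's no-on-study-assessment case applies, because its footnote disregards scans after therapy start. Duration of response, defined for responders only, disappears as well.

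**A grid.** First dose on every day of one year, randomization the day before, PD at each 6-weekly scan from Week 6 to Week 48, therapy a fixed number of days after PD. The responder column takes a response confirmed at Week 12 with PD at Week 18 or later. The lag is an assumption, since neither document gives it.

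| Days from PD to therapy | Day missing: start before PD | Year only: start before PD | Year only: confirmation lost |
|---|---|---|---|
| 1 | 93.5% | 99.5% | 59.2% |
| 7 | 73.8% | 97.8% | 57.5% |
| 14 | 50.8% | 95.9% | 55.6% |
| 21 | 27.9% | 94.0% | 53.7% |
| 28 | 4.9% | 92.1% | 51.8% |

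With only the day missing, the confirmation was lost in 0% of grid cases at every lag. All percentages are conditional on the date being partial.

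**Responder loss with only the day missing.** There are two routes:

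- Confirmation, PD and therapy fall in one calendar month. Example: confirmation 2 July, PD 30 July, therapy 31 July, imputed to 1 July. The 28 days between those scans are the edge of the visit windows (42 − 7 − 7 = 28).
- Therapy falls in the same month as the confirming scan, without PD. Example: PR on 1 September, confirmation on 14 October, radiotherapy later that month recorded as October. The imputed 1 October precedes the confirming scan.

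**Per-participant weight.** One lost responder moves an arm's ORR by 100/n points. The LAG-3 positive number per arm is not visible, so n is assumed: 100/50 = 2.0 points, and 100/125 = 0.8 points if the whole arm (250/2) were LAG-3 positive.

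**The case against.** An early start date is a defensible direction for a response endpoint, because it avoids crediting shrinkage produced by local therapy. It also suits a rule that pools on-treatment and later procedures: the protocol allows palliative radiotherapy during study, and whether a partially dated procedure came after treatment may depend on the missing part. This stands as a reason to keep the first-dose floor when timing is unclear. It does not justify that floor for a procedure recorded as subsequent therapy.

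The secondary PFS definition ignores subsequent therapy, so no imputed date can affect it. SAP 7.5.4 makes its analysis optional, however, and ORR has no equivalent protection. SAP 7.5 also describes everything beyond the primary endpoint as descriptive, which lowers the stakes for PFS but not for ORR.

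Some visibility exists: listings of subsequent therapy and of duration of response with censoring reasons, and a PFS censoring table. None is required to flag an imputed date.

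The scope is also narrow. Appendix 2 covers radiotherapy and surgery only; medication dates follow a separate specification. With only the day missing, a longer interval between PD and therapy usually puts therapy in a later month, and an imputed date equal to the PD date keeps the event.

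**Conclusion.** The point holds in a limited form. For year-only dates the rule can discard a confirmed response and censor PFS at or near randomization. For day-missing dates it can convert a documented primary-definition PFS event into censoring when therapy follows PD closely in the same calendar month. Responder loss in that second case is confined to the two routes shown.

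Three stronger readings go beyond the documents:

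- A reader might infer that post-progression therapy with a missing day commonly removes responders. The grid gives 0%.
- A reader might take the grid percentages as the share of events lost in the trial. They are conditional on a partial date and on an assumed lag. The frequency of partial dates is not given and is probably small, so no net effect on ORR or PFS can be computed.
- A reader might infer bias between arms because the trial is open-label. Nothing in the documents shows that use or dating of local therapy differs by arm.

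The PFS conclusion also assumes that subsequent anti-cancer therapy includes radiotherapy and surgery. The case for change is that a stated rule gives a demonstrably wrong result and is cheap to correct.

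**What to change.** In Appendix 2, for procedures recorded as subsequent (post-treatment) therapy, impute a partial start as the later of the present Appendix 2 date and last study dose + 1. Do not let it pass the end of the recorded month or year, and cap it at death or last known alive date. Keep the first-dose floor for procedures recorded as on-treatment or of unclear timing. Do not anchor to the PD date: that would condition the imputation on the outcome and always keep the event, even when therapy truly came first.

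Add a sensitivity analysis of BICR ORR and primary-definition PFS using the latest possible date within the recorded period. List every participant whose best response, DOR or PFS status depends on an imputed procedure date.

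Both parts are needed. Suppose the illustrative participant's last dose was Cycle 4 Day 22 of XELOX: 05MAR2019 + 147 days = 30JUL2019. A year-only entry then becomes max(05MAR2019, 31JUL2019) = 31JUL2019. The confirmed PR is restored and censoring moves from day 1 to day 127, but the event at day 169 is still missed. A latest-date analysis of the month-only entry uses 31AUG2019 and recovers that event.

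The cost is a few lines of SAP text and some programming, with no new data. A few procedures that truly began earlier may be dated late; the listing and sensitivity analysis would show them.
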